8.5 Statistical Analysis Plan

All safety and efficacy analyses will be conducted on the intent-to-treat (ITT) population, defined as all subjects who undergo treatment in either the AT or Control group. Primary effectiveness analyses be performed without imputation; that is the "ITT evaluable" dataset will include only the observed data from each study visit. Imputation of missing values (e.g., using the methodologies outlined above) will be performed for subjects who terminate prematurely or are lost to follow-up. Those dropout subjects that have device-related adverse events, or other obvious reasons that lead to negative outcomes, will be imputed as failures in the primary analysis. As a sensitivity analysis the primary effectiveness endpoint will be re-analyzed using only data from completers.

A poolability analysis and covariate analysis will be performed. The demographic characteristics as well as the two primary endpoints will be examined for poolability across sites. The impact of important covariates will be examined for the two primary efficacy endpoints. These covariates will include race, age, gender, and initial BMI.

An internal, 6-month analysis will be performed on all endpoints to ensure systematic data collection at all sites and to identify potential safety concerns. The results of this analysis will not affect the clinical investigation plan unless a previously unidentified risk to study participants is discovered.

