8.1.1 Efficacy Endpoints

The first effectiveness primary endpoint is the mean percent excess weight loss (%EWL) at 52-weeks. The hypothesis for the first primary effectiveness endpoint is that the difference in the mean percent excess weight loss (%EWL) at 52-weeks for the Aspiration Therapy (AT) group and Control group is at least 10%. %EWL is defined as absolute weight loss divided by baseline excess weight and multiplied by 100. Excess weight will be determined from ideal body weights based on a BMI=25 kg/m².

The second effectiveness primary endpoint is that at least 50% of the AT group at 52-weeks realizes a %EWL \geq 25%.

Sections 8.51 and 8.52 provide analysis of the sample size to meet co-primary endpoint #1 and #2, respectively with a power of 90% for each endpoint.

Since these endpoints are co-primary, the sample size is determined by the largest sample sizes required of the two primary endpoints. Co-primary endpoint #1 requires a sample size of 87 subjects (59 AT/ 29) to have a superiority margin of 10% EWL with a power of 90%, assuming an observed difference of 25% EWL and a standard deviation of both groups of 20%. Co-primary endpoint #2 requires a sample size of 99 AT subjects to realize that at least 50% of the AT groups realize >25% EWL at 52 weeks with a power of 90%, assuming an observed rate of 66% and a standard deviation of 20% of the AT group.

Co-primary endpoint #2 requires the largest sample sizes of the two primary endpoints, hence, not accounting for subject drop-out, a total of 150 subjects are needed in a 2:1 randomization (100 AT + 50 Control).

Since the primary analysis will be based on an ITT analysis using multiple imputations to estimate the missing values, the importance of over enrolling to have the exact number of evaluable patients has been lessened. However, to mitigate the effect of the imputation methodology on the control group, an over enrollment of ~15% for both groups is being proposed for a total enrollment size of 175 subjects (117 AT/58 Control).

8.1.2 Discussion on Drop-out Rate and Standard Deviation.

As 9% of the AT subjects (1 out of 11) in the Feasibility Study did not complete 52-weeks, we believe a 10% drop-out rate of the AT subjects for the Pivotal Study is a reasonable assumption. An over-enrollment of 15% (e.g., 117 AT subject versus 99 required) should readily accommodate the anticipated drop-out rate.

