8.1.4 Sensitivity Analyses

The efficacy analysis will be conducted on various populations for the purpose of conducting a sensitivity analysis. The first population is the per protocol population, that is, the analysis will be conducted on all treated subjects who complete the scheduled follow-up visits. A second analysis will be conducted on an intention to treat (ITT) population where the missing values at the 12 month time period will be imputed from the return to baseline methodology (i.e. all missing values at 12 months will be given the value at baseline). A third analysis used to perform efficacy analysis will use the Last Observation Carried Forward (LOCF) to impute the missing values. A fourth analysis will also be conducted: Missing values at the 12 month time period will be imputed using the mean value at 12-months of completers from %EWL quintile group such drop-out fell into at the time of drop-out. For example, if a subject were to drop-out at the 28th week and that subject fell

into the third quintile of %EWL at the 28th week, we would impute a %EWL at 52-weeks from that drop-out subject from the mean %EWL of the completers who were in the third quintile of %EWL at the 28th week. Analyses using the best and worst case scenarios will also be conducted. Finally, an analysis using multiple imputations will be conducted. In all the analyses where data is being imputed, any subject with a device related failure, or other obvious reasons that will lead to negative outcomes, will be evaluated as worst case for the AT group.

An additional sensitivity analysis for the secondary endpoints that are binary in nature will have the subjects who are lost to follow-up in the control group counted as successes and the subjects who are lost to follow-up in the AT group counted as failures.

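### Sections 8.1.1 and 8.5 contradict each other on missing week-52 weights in the primary analysis: multiple imputation in one, observed data only in the other, with some drop-outs still scored as failures

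*Protocol*

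**What the plan says.** The protocol speaks to the primary missing-data rule in three places.

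- **Section 8.1.1 (Efficacy Endpoints)** names multiple imputation and rests the modest over-enrolment on it: "Since the primary analysis will be based on an ITT analysis using multiple imputations to estimate the missing values".
- **Section 8.5 (Statistical Analysis Plan)** says "Primary effectiveness analyses be performed without imputation" and limits the dataset to observed values. The next sentence says imputation "will be performed for subjects who terminate prematurely or are lost to follow-up", with the method given only by way of example. The sentence after that takes drop-outs with device-related adverse events, "or other obvious reasons that lead to negative outcomes, will be imputed as failures in the primary analysis". The paragraph closes: "As a sensitivity analysis the primary effectiveness endpoint will be re-analyzed using only data from completers".
- **Section 8.1.4 (Sensitivity Analyses)** lists multiple imputation among the sensitivity analyses: "Finally, an analysis using multiple imputations will be conducted". It adds that, wherever data are imputed, subjects with a device failure or a similar reason "will be evaluated as worst case for the AT group".

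Section 2.1 requires both co-primary endpoints to be met for the study to succeed.

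**The concern.** An analysis cannot be free of imputation and also contain imputed failures, and it cannot be observed-only in one section and multiply imputed in another. No sentence ranks these statements. Because both endpoints must be met, a missing-data rule that changes the result on one of them changes the result of the trial.

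Three further points follow.

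- If observed-only were the primary, the completers analysis offered as a sensitivity check would use almost the same week-52 data and so would test almost nothing.
- Failure has an obvious meaning for the responder endpoint but no stated value for continuous %EWL, so the rule cannot be carried out on endpoint 1 as written.
- The catch-all category of other obvious reasons is open to judgement, and the trial is open-label.

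Missing data are expected in both arms: sections 8.1.1 and 8.1.2 plan for 10% drop-out in AT and 20% in Control.

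**Working it through.** **Inputs from the protocol.** 117 AT and 58 Control (8.1.1). Drop-out 10% AT and 20% Control (8.1.2). Endpoint 2: null 50%, expected 66%, significance level 0.025, power 90% (8.1.1, 8.5.2). Endpoint 1: margin 10, difference 25, SD 20, level 0.025, power 90% (8.1.1, 8.5.1).

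**Inputs assumed.** The number of AT drop-outs that meet the failure rule (2, 6 and 12 shown). For endpoint 1, a failure scored as 0% EWL and a Control mean of 15 (the Feasibility Trial gave 14.9). For multiple imputation, the response probability among missing subjects (0.4 and 0.6 shown).

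**Step 1: reproduce the plan's sample sizes.**

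- Endpoint 1, one-sided 0.025, 2:1: Control n = 1.5 × (1.960+1.282)² × 20² / (25−10)² = 28.02, rounded up to 29. AT is then 58 and the total 87, as in Table 8.5.1.
- Endpoint 2: n = (1.960×√(0.5×0.5) + 1.282×√(0.66×0.34))² / 0.16² = 98.4, rounded up to 99, as in Table 8.5.2.

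Both agree, so the point concerns the analysis rule and not the arithmetic of the sample size.

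**Step 2: endpoint 2.** 10% of 117 is about 12 drop-outs, leaving 105 observed. Suppose k drop-outs are scored as failures and the other drop-outs are left out. The one-sided p-value for x responders is P(X ≥ x) with X ~ Binomial(105+k, 0.5). Power is the chance that at least the required number of the 105 completers respond when each does so with probability 0.66.

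| Drop-outs scored as failures (k) | n analysed | p with 64 responders | Responders needed | Power |
|---|---|---|---|---|
| 0 (observed only) | 105 | 0.0157 | 64 | 88% |
| 2 | 107 | 0.0263 | 65 | 84% |
| 6 | 111 | 0.0642 | 67 | 72% |
| 12 (all) | 117 | 0.1776 | 70 | 49% |

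**Step 3: multiple imputation on the same 64 responders.** Let q be the response probability among the 12 missing. Then p̂ = (64+12q)/117, with approximate variance p̂(1−p̂)/117 + 12q(1−q)/117².

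- q = 0.6: p̂ = 0.609, one-sided p = 0.011, pass.
- q = 0.4: p̂ = 0.588, one-sided p = 0.033, fail.

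**Step 4: endpoint 1.** 20% of 58 is about 12, leaving 46 Control observed, against 105 AT. The observed-only standard error is 20 × √(1/105 + 1/46) = 3.54. Success needs a lower 95% limit above 10.

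- Observed difference 17: lower limit 17 − 1.96×3.54 = 10.07 (p=0.024), pass. Setting the 12 AT drop-outs to 0 gives an AT mean of 105×32/117 = 28.7 and a difference of 13.7. The lower limit is 6.8 (p=0.147), fail.
- Planned difference 25: lower limit 18.1 observed-only. With the 12 AT drop-outs at 0, the difference is 20.9 and the lower limit 13.8. Both pass.

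**The case against.** The best defence is that the text holds one awkward sentence, not a set of rival analyses. Section 8.1.4 already applies a worst-case rule inside imputed analyses, so multiple imputation and the failure rule fit together. The sentence on early terminations in 8.5 could mean that isolated missed visits are left alone while drop-outs are imputed. On that reading the completers analysis is a real sensitivity check. This stands in part: multiple imputation plus the failure rule is the better supported primary, and a reader who counts three mutually incompatible rules goes too far. It does not remove the conflict, because 8.5 says in terms that the primary uses no imputation and only observed data.

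Some stronger readings are also unsupported.

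- *Any result from 64 to 69 responders passes under one stated rule and fails under the other, with power of 49%.* This scores all 12 AT drop-outs as failures. Section 8.5 fails only those with device-related adverse events or other obvious reasons, so 12 is the extreme.
- *Endpoint 1 is equally exposed.* At the planned difference both rules pass. The 17-point case also zeroes AT drop-outs only.
- *Observed-only analysis favours AT.* This is not shown for endpoint 1. Control drop-out is assumed to be twice that of AT, and losing poorly responding controls would raise the observed Control mean.
- *The failure rule will be applied with arm and weights known.* The protocol does not say who applies it. The open-label design makes this possible, no more.

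**Conclusion.** The contradiction is real and sits in the current text. It is not a detail left for a later document, since any later plan would have to overrule one of the protocol's own statements. It should be corrected before analysis, because the primary analysis of both co-primary endpoints is not uniquely defined.

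The size is material for endpoint 2. At the bare pass mark, two drop-outs counted as failures reverse the result, and power falls from 88% to 84% with 2 and 72% with 6, with 49% as the lower bound. Multiple imputation against observed-only is a milder contrast: at 64 responders it changes the result only if missing subjects respond clearly less often than completers. For endpoint 1 a reversal appears only near an observed difference of 17, given SD 20 and a failure scored as 0% EWL. The number of drop-outs meeting the failure rule is not in the protocol, so these figures show a range and are not a forecast.

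**What to change.** In section 8.5, delete the sentence that excludes imputation and state one primary rule that agrees with 8.1.1:

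1. Intention-to-treat analysis with multiple imputation of missing week-52 weights, using arm, the stratification factors and earlier weights.
2. Subjects with a missing week-52 weight who dropped out for an adjudicated device-, procedure- or therapy-related adverse event are scored as non-responders, with a stated %EWL value for endpoint 1 (for example 0%).
3. That closed list replaces the open category of other obvious reasons and is applied without sight of weights. The existing Safety Adjudication Committee (section 7.4) could do this.
4. Observed week-52 weights are never overwritten. Tube removal alone should not trigger a score of 0, because the protocol goes on collecting weights after removal (sections 3.0 and 5.8).

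In section 8.1.4, remove multiple imputation from the sensitivity list. Keep observed-case/completers, return to baseline, last observation carried forward and worst case there.

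The cost is wording only. The AT estimate and the endpoint-2 power will be somewhat less favourable than under observed data, by an amount that depends on how many drop-outs meet the closed list.

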This is a multi-center, randomized, controlled, open-label, 52-week trial to support FDA premarket approval with additional long-term safety and efficacy monitoring of the treatment group for post market reporting and publication purposes. Eligible subjects will be randomized in a 2:1 (treatment: control) ratio to treatment with the Aspiration Therapy (n=117) or lifestyle therapy (behavior education, diet and exercise) program (n=58). The AspireAssist™ Aspiration Therapy System involves percutaneous endoscopic placement of a gastric device that permits aspiration of a portion of stomach contents after meals, in conjunction with lifestyle therapy.

Aspiration Therapy subjects who lose and maintain at least 10% weight loss from baseline will be given the option to continue in the study for an additional four years after the 52-weeks of therapy.

Primary Outcomes:

The first effectiveness primary endpoint is the mean percent excess weight loss (%EWL) at 52-weeks. The hypothesis for the first primary effectiveness endpoint is that the difference in the mean percent excess weight loss (%EWL) at 52-weeks for the Aspiration Therapy (AT) group and Control group is at least 10%. %EWL is defined as absolute weight loss divided by baseline excess weight and multiplied by 100. Excess weight will be determined from ideal body weights based on a BMI=25 kg/m².

The second effectiveness primary endpoint is that at least 50% of the AT group at 52-weeks realizes a %EWL \geq 25%.

Both primary endpoints must be met for the study to be considered a success.

Secondary Outcomes (at 52-weeks)

i) Mean percent absolute weight loss in AT compared to Control group, ii) proportion of subjects who achieve ≥10% absolute weight loss in AT compared to Control group, iii) mean percent change serum lipids (triglyceride, HDL-cholesterol and LDL-cholesterol concentration) in the AT group compared to the control group; iv) mean percent change in systolic and diastolic blood pressures in the AT group compared to the control group; v) "Impact of Weight on Quality of Life" (IWQOL) questionnaire; vi) change in mean hemoglobin A1C (only subjects with T2 diabetes at baseline) , vii) percent procedural success (defined as successful endoscopic placement of the A-Tube) in all subjects undergoing endoscopy; viii) mean percent change in medications

Safety Outcomes:

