5.5.9 Lifestyle Therapy

The behavioral weight loss program (see **Appendix C**) is a 10-session program delivered individually or in a group to each research subject during the first 52-weeks and includes nutritional, physical activity, and behavioral education topics. AT and Control Subjects are instructed to have a balanced 300 and 600 kcal-deficit diet, respectively. Initial daily energy requirements can be estimated by using the Mifflin-St Jeor equations⁵⁵ to estimate resting energy expenditure in men and women (see below) multiplied by an activity factor of 1.4:

```
Men: Resting Energy Expenditure = (10 x weight in kg) + (6.25 x height in cm) - (5 x age in yrs) + 5

Women: Resting Energy Expenditure =
```

(10 x weight in kg) + (6.25 x height in cm) - (5 x age in yrs) - 161

Subjects are also instructed to establish a structured eating plan, which involves eating three meals a day, eating slowly and chewing food well, drinking a minimum of 500 mls of non-caloric fluid with each meal and at least 2000 mls of fluid per day (including the fluid consumed at meals, and limiting snacking between meals. Physical activity topics include the health benefits of physical activity and strategies for increasing lifestyle activity. The behavioral program emphasizes strategies of self-monitoring and goal-setting, and includes problem-solving, dealing with high-risk situations / cues for unhealthy eating, and stress management.

These Lifestyle Therapy sessions will be given individually during the same visit as the Medical & Study visits or regularly in group sessions.

If a subject in either intervention group is struggling with adherence or

compliance to the therapy, an individual session may be arranged between the subject and a behavioral consultant or another subject from their intervention group who has been successful with the therapy. Meetings will be considered and arranged on an individual basis with the intention of assisting subjects who may require additional attention to address a particular barrier to success with the study intervention. Any such meetings will only be held if the subject is so willing and will require permission, in advance, from the Sponsor.

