7.4 Data and Safety Monitoring

Data from the study will be monitored on a continuous basis by the study team (PI, co-investigators, and study research nurse/coordinator). The study team will meet regularly to review subject progress, adverse events (AEs), laboratory values, and any study issues. The local IRB and the Sponsor will be notified of AEs/SAEs as stated in section E3 of this protocol. Information regarding SAEs occurring at any site will be disseminated by the Sponsor to all study sites and the information reported to the IRB. If, at any time during the study, an unanticipated significant risk to study subjects is identified, study recruitment and/or the study intervention may be stopped until such

risk has been satisfactorily resolved or corrective action taken and all study documents updated, as needed. The need to stop or interrupt study activity will be determined by the Sponsor and PI.

To ensure consistency in reporting adverse events and to meet the ethical responsibilities and standards for research subjects, a Safety Adjudication Committee (SAC) has been formed. The SAC is composed of a group of independent physicians who have no financial interest in the Sponsor (or a competitor to Sponsor) and who have expertise in gastrostomy tubes, metabolism, and obesity. The responsibilities of this committee are described in the Investigators' Brochure.

Confidentiality. All of the data will be treated confidentially and the subjects' names and identities will not be disclosed in any published reports. Subjects are assigned a study specific identifying number upon entry to the study, after which all medical information is referenced by this number. Clinic records are maintained in locked file cabinets within a locked room.

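### The internal 6-month analysis covers all endpoints, wider than its stated purposes need, and nothing requires the contradictory primary missing-data rule to be settled before it is run

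*Protocol*

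**What the plan says.** **The 6-month analysis.** Section 8.5 says "An internal, 6-month analysis will be performed on all endpoints", and gives its purpose as "to ensure systematic data collection at all sites and to identify potential safety concerns". The next sentence limits its use: "The results of this analysis will not affect the clinical investigation plan unless a previously unidentified risk to study participants is discovered". The section does not say whether results are shown by arm or pooled, and beyond the word internal it does not identify the recipient.

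**Setting.** The synopsis describes the design: "This is a multi-center, randomized, controlled, open-label, 52-week trial". On halting the study, section 7.4 says "The need to stop or interrupt study activity will be determined by the Sponsor and PI". The independent committee in that section is a safety adjudication committee; it is not described as receiving interim efficacy.

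**The primary missing-data rule.** Section 8.1.1 says that "the primary analysis will be based on an ITT analysis using multiple imputations". Section 8.5 says "Primary effectiveness analyses be performed without imputation", with the evaluable dataset confined to observed data. It then says that values will be imputed for subjects who terminate early or are lost, and that drop-outs with device-related adverse events or other obvious reasons for a bad outcome count as failures in the primary analysis. Section 8.1.4 lists multiple imputation among the sensitivity analyses.

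**The concern.** The scope is wider than the purpose. Completeness of endpoint data can be checked with the arms pooled, and safety can be reviewed by arm without weight-loss results. As written, the analysis could also produce mean percent excess weight loss (%EWL) by arm and the AT responder rate, months before the 52-week endpoint.

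That would matter little if everything that turns data into the primary result were already fixed. It is not: several incompatible treatments of missing data are each supported by some sentence of the protocol. Someone who had seen 6-month efficacy and drop-out could later adopt any of them and remain within the document. Both co-primary endpoints must succeed, so a rule that shifts either one bears on the trial's conclusion.

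**Working it through.** **1. What each purpose needs, against what is planned**

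- Consistent data collection at all sites: needs presence, timing and plausibility of each endpoint's data by site. Arms can be pooled.
- Safety: needs adverse events and laboratory results by arm. No efficacy comparison is needed.
- Planned scope: all endpoints, which takes in the efficacy endpoints of sections 2.1 and 2.2. Taken literally, this cannot be met at 6 months: the co-primaries are defined at 52 weeks, and Tables 1 and 3 schedule the quality-of-life questionnaire only at screening and week 52.

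**2. What the assurance covers**

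It bars changes to the plan. Choosing between two sentences already in the plan is not clearly a change to it. The assurance therefore leaves open which missing-data rule governs.

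**3. Reproducing the plan's figure for endpoint 2**

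Inputs (sections 8.1.1 and 8.5.2): null 50%, expected 66%, significance level 0.025 (taken as one-sided), power 90%.

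n = [1.960 × √(0.5 × 0.5) + 1.282 × √(0.66 × 0.34)]² / (0.66 − 0.50)² = (0.980 + 0.607)² / 0.0256 = 98.4, rounded up to 99.

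This matches Table 8.5.2, so no sample-size error is involved.

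**4. How far the missing-data rule could move endpoint 2**

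Inputs: 117 AT subjects, 66% responders among completers, 10% AT drop-out (sections 8.1.1 and 8.1.2). Exact one-sided binomial test against 50%.

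- All 117 with an outcome: success needs at least 70 responders, 70/117 = 59.8% (exact level 0.021; power at 66% about 93%).
- Observed data only: 117 × 0.90 ≈ 105 subjects, success at 64 or more, power about 88%. Expected rate 66%.
- Multiple imputation, if drop-outs resemble completers: expected rate again about 66%. The 70/117 boundary is then only approximate, because imputation adds variance.
- Every drop-out a failure (outer bound): 0.90 × 0.66 = 59.4%, or 69.5 responders expected against 70 needed; power about 50%. At an illustrative 15% drop-out, 0.85 × 0.66 = 56.1% and power is about 24%.

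**5. How much of the outer bound the named rules reach**

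Section 8.5 fails only some drop-outs. Let f be the share of drop-outs failed, and give the rest the completer rate. The expected rate is 0.66 × (1 − 0.10 f).

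- f = 0.5 gives 0.66 × 0.95 = 62.7%, above the boundary.
- The rate falls to 59.8% when 1 − 0.10 f = 0.598/0.66 = 0.9065, so f = 0.0935/0.10 ≈ 0.94.
- At 15% drop-out the same step gives f = 0.0935/0.15 ≈ 0.62.

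At the protocol's own drop-out rate, the expected rate reaches the boundary only if nearly all drop-outs are failed.

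**The case against.** The case against is substantial, and much of it stands.

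- **By-arm efficacy reaching the sponsor is an inference.** A reader might conclude that the sponsor will receive a between-arm comparison. The text says only that the analysis is internal and covers all endpoints. Recipients and table layouts are commonly left to a separate analysis plan, which is not at hand. What can be said is that the protocol fixes a broad scope without restricting it.
- **A reader might infer inflated type I error.** The documents do not support that. There is no stopping rule for efficacy, no sample-size change and no test attached to this analysis.
- **A reader might see sponsor approval of extra sessions as a lever.** Section 5.5.9 says such meetings "will require permission, in advance, from the Sponsor". They are open to a struggling subject in either group, are arranged individually and depend on that subject's adherence. Approval works as a per-subject check, and the text does not tie it to aggregate results.
- **The assurance may reach further than allowed here.** Section 1.3.4.2 uses the same term, clinical investigation plan, for the document on which staff are trained. That would include the statistical section, but a document that contradicts itself still gives no single rule to hold to.
- **Access already exists.** In this open-label trial, section 5.5.2 has the medical consultant, who signs for the sponsor, monitoring each subject's weight loss, and section 11.5 gives sponsor monitors online access to case report forms. Endpoint 2 concerns the AT arm alone, so it can be gauged without a comparison. A pooled table does not remove this; the 6-month analysis adds a planned aggregate to it.
- **The missing-data contradiction is a defect in its own right.** It would need correcting without any 6-month analysis. That is why reconciling the rule comes first in the fix.

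**Conclusion.** The point holds in a limited form. The 6-month analysis is broader than its two stated purposes require. The protocol does not restrict its efficacy content, and it leaves the primary missing-data rule contradictory at the time the analysis would be run. This is a wording correction worth making; it does not show that the trial's error rate or conduct is compromised.

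The 59.4% against 59.8% comparison is an outer bound and rests on 117 AT subjects, a 66% completer rate, 10% drop-out and every drop-out failed. None of the primary rules in sections 8.1.1 and 8.5 fails every drop-out. If drop-outs resemble completers, observed-data analysis and multiple imputation both sit near 66%. A reader might take the bound as evidence that the choice between the named rules would decide the trial; the documents do not show that. They show that the rule can matter, which is enough reason to fix it before any efficacy summary exists.

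**What to change.** 1. Reconcile sections 8.1.1, 8.1.4 and 8.5 to one primary missing-data rule for both co-primary endpoints. State which drop-outs, if any, count as failures, and move every other method to the sensitivity analyses. Fix this before the 6-month analysis is run.
2. In section 8.5, replace the reference to all endpoints with: safety by arm, and data completeness and efficacy pooled across arms. State who receives the output.

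**Cost.** Wording only; sample size, significance level and power are unchanged, and both stated purposes are kept. The sponsor gives up an early comparative look at efficacy. The change does not close off the access to individual weights that the open-label design already gives.
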